2.2.2 Additional eligibility criteria

- Inclusion criteria:

- Unilocular pleural collection

- Exclusion criteria:

- Known or suspected thyroid disease
- Allergy to iodine
- Persistent large collection on follow up imaging 24-48 of post tube insertion that is deemed to require another drainage procedure

2.2.3 Specific assessments

- Two applications of 100-250 ml solution of 2% povidone-iodine will be irrigated into the pleural space of eligible patients 12 hours apart. The tube will be clamped for 15 minutes after irrigation and the patient will be asked to change position frequently during this period. The first dose will be applied 24-72 hours after tube insertion.

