2.2.1 Rationale and design

The antiseptic povidone-iodine can safely be instilled into the pleural for the purpose of pleurodesis^[6]. Pleural irrigation with antiseptics is used in adults with open drainage for chronic empyema^[7] and has been described in the acute management of paediatric pleural infection^[8].

This sub-study will investigate the safety and usefulness of povidone-iodine pleural irrigation in 15 eligible patients recruited to PICS. A matched control group will be used and will be composed of 15 patients previously recruited to PICS without receiving povidone-iodine pleural irrigation.

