2.2.4 Outcomes

- Safety: incidence of adverse events (new chest pain, fever, dyspnoea or desaturation) within 24 hours from the first irrigation

- Efficacy

- Time to defervescence
- Time to chest tube removal
- Length of hospital stay
- Need for additional aspiration/tubes

_ Failure of medical treatment

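### The second povidone-iodine irrigation is scheduled 12 hours after the first with no condition on how the patient tolerated the first

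*Protocol*

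**What the plan says.** The regimen is in protocol section 2.2.3: "Two applications of 100-250 ml solution of 2% povidone-iodine will be irrigated into the pleural space of eligible patients 12 hours apart". The same section adds the dwell procedure, "The tube will be clamped for 15 minutes after irrigation and the patient will be asked to change position frequently during this period", and the start time, "The first dose will be applied 24-72 hours after tube insertion".

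Section 2.2.4 defines the safety outcome: "Safety: incidence of adverse events (new chest pain, fever, dyspnoea or desaturation) within 24 hours from the first irrigation". It also lists "Time to defervescence" among the efficacy outcomes.

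Section 2.2.2 gives the entry criteria, one of whose exclusions is "Allergy to iodine". Section 2.2.1 starts from the position that "The antiseptic povidone-iodine can safely be instilled into the pleural for the purpose of pleurodesis", and then sets the aim: "This sub-study will investigate the safety and usefulness of povidone-iodine pleural irrigation in 15 eligible patients recruited to PICS".

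No section states a rule for withholding, stopping or modifying the irrigation once the first application has been given.

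**The concern.** The protocol names the acute events it regards as possible harms of irrigation and has staff look for them over 24 hours. It places the second exposure in the middle of that period and ties no action to what is found. A patient who became hypoxic, breathless or had marked chest pain after the first application is still scheduled for up to 250 ml more, with the tube closed for another 15 minutes.

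This is mainly a matter of participant safety. It also affects consistency. If staff do withhold, each does so on a personal threshold, and with 15 treated patients a few such decisions change what regimen was actually studied.

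A rule on when to give or hold a dose belongs in the protocol. It cannot be assumed to sit in an unseen analysis plan.

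**Working it through.** There is no planned figure to reproduce. The check is one of timing and text.

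**Inputs**
- Two applications, 12 hours apart, 100-250 ml each, 15-minute clamp (section 2.2.3).
- First application 24-72 hours after tube insertion (section 2.2.3).
- Safety window of 24 hours from the first irrigation (section 2.2.4).
- 15 irrigated patients (section 2.2.1).

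**Timing.** Take the first irrigation as hour 0. The second falls at hour 12 and the safety window closes at hour 24. So 12 hours of the window precede the second application and 24 − 12 = 12 hours follow it. Events in hours 0-12 are therefore already within what staff must ascertain, and are known, or could be, when the second application is due.

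**Exposure.** One application is 100-250 ml. Two give 2 × 100 = 200 ml to 2 × 250 = 500 ml, and 2 × 15 = 30 minutes of clamping in total.

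**Which existing limits respond to an event in hours 0-12?**

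| Provision | Section | Responds to an event after the first application? |
|---|---|---|
| Unilocular collection; thyroid disease | 2.2.2 | No, assessed at entry |
| Iodine allergy | 2.2.2 | Written for entry; at most it could be read to cover an iodine reaction |
| Persistent large collection on imaging after tube insertion | 2.2.2 | No, it concerns the need for further drainage |
| Delay of 24-72 hours before the first dose | 2.2.3 | No, it precedes the first application |
| 15-minute clamp | 2.2.3 | No, it is the same for both applications |
| Safety outcome | 2.2.4 | Counts the event but attaches no action |

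None covers desaturation, dyspnoea or chest pain after the first application.

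**Cost of a rule, in applications.** Planned: 15 × 2 = 30. If k patients have the second withheld, 30 − k are given. The protocol gives no basis for k, so the values are illustrative:
- k = 1: 29 given, 1/30 = 3.3% fewer.
- k = 2: 28 given, 2/30 = 6.7% fewer.
- k = 3: 27 given, 3/30 = 10% fewer.

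A patient withheld for a listed event has already been counted under section 2.2.4. Withholding therefore does not remove that patient from the number with any listed event.

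**The case against.** The strongest reply is that section 2.2.3 states a nominal schedule for inpatients under clinical care. It does not say that the second application must be given whatever happens, and no sensible clinician would irrigate a patient in respiratory difficulty. This is largely true, and it limits the point: the protocol does not override bedside judgement. What remains is that the written regimen is unconditional and the judgement has no stated criterion.

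A second reply is that the agent's safety is already asserted in section 2.2.1. That statement concerns pleurodesis, and the same section makes the safety of this irrigation a study question.

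A third is that the iodine-allergy exclusion ends eligibility after a reaction. That is a fair reading for iodine reactions and for nothing else on the safety list.

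A reader might also infer more than the text supports:
- *That the safety rate has an unclear denominator.* Section 2.2.4 counts time from the first irrigation, so the natural denominator is everyone who received one. The protocol does not invite restriction to patients given both.
- *That withheld applications would go unrecorded.* Section 2.1.5 already has treatment data collected for all cohort participants. The item is general and does not ask for the number of irrigations or the reason for withholding, but treatment recording is not absent.
- *That a second application after an event is shown to be harmful, or that the situation is likely to arise.* The documents contain no event rates and no evidence on re-exposure. Any probability would rest on an assumed rate for a withholding criterion that has not yet been defined.

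**Conclusion.** The point holds as a gap in the dosing instruction. The second application falls at hour 12 of a 24-hour safety window and is not conditional on tolerance of the first. The only provision that could respond is the iodine-allergy exclusion, and that only by extension. Followed as written, the plan re-exposes and re-clamps a patient who has just had one of the events under study.

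Its size in harm cannot be stated from the documents. Nor can the effect on the efficacy comparison be bounded without assuming how benefit differs between patients in whom the second application is withheld and the others. The conclusion rests on the text and the timing alone, and on reading the unqualified reference to eligible patients as all 15 irrigated patients.

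The protocol should be changed: the gap concerns participant safety and costs very little to close. It does not invalidate the design.

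**What to change.** In section 2.2.3, add a documented bedside check immediately before the second application. Withhold that application if either of these applies:
- new desaturation, new or worsening dyspnoea, or significant new chest pain since the first application is unresolved at the check, or was serious even if it has resolved;
- an iodine reaction is suspected.

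The investigators should set the clinical thresholds before enrolment. A brief symptom that has cleared and was not serious need not cancel the second application. Fever alone need not do so either: time to defervescence is an efficacy outcome, so fever is expected in this population. New fever would still be counted under section 2.2.4.

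Record for each irrigated patient whether one or two applications were given and, if one, why.

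The cost is a few sentences and one check per patient, with no added procedure, committee or participants. The downside is that a few patients receive only one application, some perhaps for symptoms unrelated to the irrigation, and this may slightly dilute the efficacy comparison.

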2.2.4 Outcomes

- Safety: incidence of adverse events (new chest pain, fever, dyspnoea or desaturation) within 24 hours from the first irrigation

- Efficacy

- Time to defervescence
- Time to chest tube removal
- Length of hospital stay
- Need for additional aspiration/tubes

_ Failure of medical treatment

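### The irrigation safety outcome leaves out worsening of existing symptoms and other reactions, is unclear on what must be new, and has no pre-irrigation reference

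*Protocol*

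**What the plan says.** Section 2.2.1 names safety first among the sub-study's aims: "This sub-study will investigate the safety and usefulness of povidone-iodine pleural irrigation". It plans "povidone-iodine pleural irrigation in 15 eligible patients recruited to PICS" and a matched control group of "15 patients previously recruited to PICS without receiving povidone-iodine pleural irrigation".

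Section 2.2.4 contains the only safety outcome: "Safety: incidence of adverse events (new chest pain, fever, dyspnoea or desaturation"), counted "within 24 hours from the first irrigation". The efficacy list in the same section opens with "Time to defervescence". Section 2.2.2 lists "Allergy to iodine" among the exclusions.

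Section 2.2.3 is headed as assessments but describes only the irrigation procedure and its timing. The data list for the parent cohort in section 2.1.5 covers comorbidities, a risk score, blood tests, pleural fluid and microbiology, imaging, treatments, length of stay and outcome at discharge. Neither section names a reading of pain, temperature, dyspnoea or oxygen saturation.

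**The concern.** An event that must be new needs a reference point, and the protocol does not give one. The wording can be read in two ways, and each miscounts some patients.

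- If *new* covers all four events, a patient who already has one of them when irrigated cannot score that event, however much it worsens.
- If *new* covers chest pain only, fever that is simply the infection continuing can be scored as an adverse event.

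The list is also limited to four items. A hypersensitivity reaction without dyspnoea or desaturation falls outside it, unless it shows itself as chest pain or fever. Yet the allergy exclusion shows that a reaction to iodine was foreseen.

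What is at stake is the accuracy of a safety count in 15 treated patients. With so few, every patient who cannot contribute an event takes away a visible share of the information.

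**Working it through.** **No figure to reproduce.** The protocol gives no expected event rate, safety threshold or derivation of the 15 per group. The check is therefore a reading of the sections against each other, followed by an illustration under a stated assumption.

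**Reading the sections together**

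1. Fever: section 2.2.4 uses time to defervescence as an efficacy outcome, so some patients are expected to have fever from the infection. The same sign appears in the safety outcome. The overlap is documented.
2. Chest pain, dyspnoea and desaturation: overlap with the disease is an inference from the population (inpatients with pleural infection and a chest tube). The protocol does not state it.
3. Baseline: sections 2.1.5 and 2.2.3 list no pre-irrigation reading of any of the four, so what counts as new is not tied to anything.

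**Reading A: *new* governs all four events**

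Inputs: 15 treated patients (section 2.2.1). The share *s* who already have a given symptom is not in the document, so it is assumed to range from 0% to 80%.

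- Number able to develop that symptom: m = 15 × (1 − s)
- Upper one-sided 95% bound on the event rate if none of the m has the event: 1 − 0.05^(1/m)
- Chance of seeing at least one event if the true rate is 10% (an assumption): 1 − 0.9^m

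| Assumed s | m | Upper bound after 0 events | Chance of at least 1 event at 10% |
|---|---|---|---|
| 0% | 15 | 18.1% | 79% |
| 20% | 12 | 22.1% | 72% |
| 40% | 9 | 28.3% | 61% |
| 60% | 6 | 39.3% | 47% |
| 80% | 3 | 63.2% | 27% |

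If worsening counted as well, all 15 would stay at risk for every symptom, and the first row would apply whatever the value of s.

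These figures are for one symptom at a time. A patient already in pain can still score new fever, dyspnoea or desaturation, so the loss for the four events combined is smaller than the table shows for any one of them.

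**Reading B: *new* governs chest pain only**

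If a share f of the 15 is still febrile from the infection during the window, 15 × f patients score a fever event whether or not irrigation contributed. Over the same assumed range of 0% to 80%, that is 0 to 12 of 15.

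Reading A errs towards too few events and reading B towards too many. The protocol does not settle which applies.

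**The case against.** Several objections deserve weight.

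- **New onset is a recognised way to separate treatment effects from background disease.** This is correct, and events in patients without the symptom are still counted. But the convention needs a baseline reading, and it leaves out worsening unless worsening is added.
- **Reading B is strained.** Adverse events timed from the irrigation suggest events that arise after it. That makes reading A the more natural one, but it does not settle the wording, and under reading A worsening is lost.
- **Overlap with the disease is shown for fever only.** This stands. Patients are treated 24 to 72 hours after tube insertion, have unilocular collections, and are excluded if a large collection persists and is judged to need another drainage procedure. The share with pain, dyspnoea or desaturation at irrigation could be low, which is why the range starts at 0%.
- **The control group gives the background rate.** It could do so in principle. However, controls have no first irrigation from which to start the 24-hour window, and section 2.1.5 does not list these observations for them. A comparison also cannot restore worsening events that the definition leaves out.
- **The case report form or a statistical analysis plan may hold the detail.** Either may. A later analysis plan can define worsening, but it cannot supply a bedside reading that was not taken, and the outcome as the protocol states it does not count worsening.
- **The protocol does not say that other events go unrecorded.** This is true. The point is narrower: such events are not part of the stated safety outcome.

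A reader might go further and infer that the sub-study cannot judge safety, or that the miscount could overturn its conclusion. The documents support neither. New-onset events are still captured, and the protocol states no safety threshold or decision rule that could be overturned.

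**Conclusion.** The concern holds as a weakness in how the safety outcome is defined, and it is worth correcting. As written, the outcome does not count worsening of an existing symptom, is ambiguous about which events must be new, and leaves out any other reaction. No pre-irrigation reading is listed to anchor it. The consequence is a less sensitive or a contaminated safety count, depending on the reading.

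The size cannot be fixed from the protocol, because it gives no baseline symptom rate. Under reading A, the assumed 0% to 80% already symptomatic moves the zero-event upper bound for a single symptom from 18% to 63%. That is an illustration of direction and range, not an estimate.

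**What to change.** In section 2.2.3, add a record of pain score, temperature, dyspnoea grade and oxygen saturation before the first irrigation, and again before the second.

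In section 2.2.4, define each of the four events as new, or worsened by a pre-specified amount, relative to the reading before the first irrigation. Keeping that reading as the reference throughout prevents a symptom provoked by the first application from becoming the baseline for the second. The pre-specified amount is needed so that not every small change counts. Add hypersensitivity reactions and any other adverse event to the outcome.

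The cost is one set of bedside observations per irrigation in 15 inpatients, with matching lines on the case report form. The reported event rate may rise and will include some ordinary fluctuation. The change does not by itself give the controls a comparable baseline or time origin, so the treated group's count should not be compared with theirs as if it did. No dose, schedule or treatment rule is affected.

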2.1.5 Study assessments

PICS is a strictly observational study and all data gathered will be related to the patient's clinical care. The following data will be collected:

- Average age and gender proportion of patients admitted (from screening log)
- Comorbidities
- RAPID score
- Baseline blood tests and follow up inpatient tests (minimum urea and electrolytes, full blood count, C-reactive protein, and serum albumin)
- Pleural fluid results
- Microbiological results (pleural fluid and blood)
- Ultrasound findings
- CT findings if available
- Baseline and follow up CXRs
- Treatments received for pleural infection
- Length of hospital stay (LOS)
- Outcome at discharge (medical, surgical, dead)

Medical treatment will include: thoracentesis, chest drain, fibrinolytic, medical thoracoscopy

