4.0 Statistics

Continuous variables will be compared between the study arms using t-test or Mann Whitney test according to the normality of the study data. Categorical variables (including primary outcome measure) will be compared using the Chi squared test or Fisher exact test as appropriate.

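### The only safety outcome closes 24 h after the first of two irrigations given 12 h apart, so the second irrigation is observed for only about 12 h

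*Protocol*

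**What the plan says.** Section 2.2.1 sets the aim: "This sub-study will investigate the safety and usefulness of povidone-iodine pleural irrigation in 15 eligible patients recruited to PICS". Safety comes first in that aim.

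Section 2.2.3 describes the intervention: "Two applications of 100-250 ml solution of 2% povidone-iodine will be irrigated into the pleural space of eligible patients 12 hours apart". After irrigation the tube is clamped for 15 minutes.

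Section 2.2.4 lists one safety outcome: "incidence of adverse events (new chest pain, fever, dyspnoea or desaturation) within 24 hours from the first irrigation". The remaining outcomes there are efficacy outcomes, among them "Time to defervescence". The protocol gives no separate observation period for the second irrigation and describes no later collection of adverse events.

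**The concern.** The treatment under test is the two-irrigation course, and a patient has received all of it only once the second irrigation is given. The safety window is tied to the first irrigation, so it follows the completed course for half as long as it follows the first irrigation alone. The protocol allots 24 h after the first irrigation and gives no reason for a shorter period after the second.

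A patient who first desaturates 14 h after the second irrigation, for example, would enter the results as having had no adverse event. Because the protocol fixes the window, this is not a detail left open for a later analysis plan. Events that were never entered on the case report form cannot be restored at analysis. At stake is whether the incidence reported for the sub-study's first-named aim describes the whole course or is somewhat too low.

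**Working it through.** **Inputs from the protocol.** Window: 24 h from the first irrigation (2.2.4). Two irrigations, 12 h apart, each with a 15-minute clamp (2.2.3). Treated patients: 15 (2.2.1). There is no event rate, onset time or sample-size calculation to reproduce.

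**Timeline**
- Observation after the first irrigation: 24 h.
- Observation after the second: 24 - 12 = 12 h, or 11.75 h after its clamp is released. A late second irrigation shortens this further.
- End of a 24 h period after the second: 12 + 24 = 36 h after the first.
- Share of that span observed: 24/36 = 67%. Hours 24 to 36 are not observed.

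**Do other listed items fill the gap?** Time to defervescence follows fever in part. Additional aspiration or tubes, failure of medical treatment, length of stay and outcome at discharge (2.1.5, 2.2.4) run past 24 h and may catch some serious consequences. None of them records new chest pain, dyspnoea or desaturation.

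**Possible size, under assumptions that are not in the protocol.** Let p be the risk of a reaction to each irrigation, and r the within-patient correlation between reactions to the two. Suppose all reactions start within 24 h of an irrigation, and a share f start after 12 h whether or not the patient reacted to the first. Then:
- P(no reaction to the first, reaction to the second) = p(1-p)(1-r)
- full incidence = p + p(1-p)(1-r)
- uncounted incidence = p(1-p)(1-r)f

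For example, p = 0.10, r = 0, f = 0.50 gives 0.10 × 0.90 × 1 × 0.50 = 0.045, and 15 × 0.045 = 0.68 patients.

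| p | r | Full incidence | Uncounted, f = 10% | f = 25% | f = 50% |
|---|---|---|---|---|---|
| 10% | 0 | 19.0% | 0.9 points (0.14 of 15) | 2.3 (0.34) | 4.5 (0.68) |
| 10% | 0.5 | 14.5% | 0.5 (0.07) | 1.1 (0.17) | 2.3 (0.34) |
| 20% | 0 | 36.0% | 1.6 (0.24) | 4.0 (0.60) | 8.0 (1.20) |
| 20% | 0.5 | 28.0% | 0.8 (0.12) | 2.0 (0.30) | 4.0 (0.60) |

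The loss is zero if f = 0 (no late onset) or r = 1 (the same patients react both times).

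**Precision for scale.** One patient is 1/15 = 6.7 percentage points. The exact (Clopper-Pearson) 95% intervals are 1.7% to 40.5% for 2/15 and 4.3% to 48.1% for 3/15.

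**The case against.** Sections 2.2.3 and 2.2.4 do not contradict each other. The second irrigation lies inside the window, and any finite window leaves some later events uncounted. That is right, and it makes this a weak design choice rather than an inconsistency.

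The 67% rests on a 36 h benchmark that the protocol does not set. Counted per irrigation, 24 + 12 = 36 of 48 hours are observed, or 75%. Both figures are correct for the span each defines, and the 12 h against 24 h difference does not depend on the choice.

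The larger scenarios are generous. f = 50% means onset spread evenly over 24 h with no clustering near the irrigation, and r = 0 means reactions in the same patient are independent. The only scenario above one patient needs both. This stands, and it is why the effect is judged probably small. The protocol also ties no threshold or decision to this incidence.

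The outcome does not attribute symptoms to irrigation. In patients with active infection and a chest tube, background events can already push the count above the harm caused by irrigation, and a longer window adds more. This stands: the one-way direction applies to the count of listed events, not to irrigation-caused harm.

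An extended window would give 36 h to patients with two irrigations and 24 h to those with one, and controls have no irrigation to anchor a window. The first is a real but modest drawback. The second exists under the present rule as well, so it is neither created nor solved by the change.

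**Conclusion.** The concern holds. The protocol's only safety outcome observes the second irrigation for 12 h against 24 h for the first, and nothing else listed records later new chest pain, dyspnoea or desaturation. This follows directly from the two sections and needs no assumption beyond the stated 12 h interval.

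The number of events missed cannot be derived from the protocol. In the scenarios tabulated the uncounted incidence runs from about 0.5 to 8 percentage points, with 11 of the 12 below one patient. The overlap of the intervals for 2/15 and 3/15 shows that one missed patient would hardly change the safety conclusion. The change is worth making because it is cheap and closes a gap in the sub-study's only safety measure, not because a material bias has been shown.

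**What to change.** Leave the irrigation schedule unchanged. In 2.2.4, define the safety outcome as any of the four listed events with onset from the first irrigation until 24 h after the last irrigation received. For a patient who receives only one irrigation this equals the present rule.

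Report the treated-arm result as a proportion with an exact 95% confidence interval, and state that it includes background events from the disease or the tube. The comparisons planned in 4.0 can stay as written.

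The cost is one line of text and about 12 more hours of inpatient adverse-event recording per treated patient (15 × 12 = 180 patient-hours). The downside is that the longer window will take in some extra chest pain, fever and dyspnoea unrelated to the irrigation.
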